### Analysis plan for primary and secondary endpoints:

The objective is to compare the change in the primary and secondary endpoints over time between the two treatment groups.

Descriptive analysis techniques will be used to characterize study participants. Center and variability of continuous variables will be presented as means (SD) when they follow a normal distribution and as medians and interquartile range otherwise. Log transformation will be applied on variables with skewed distribution.

The primary endpoint is change in the phosphocreatine recovery time (s). Secondary endpoints are 1) change in six-minute walk distance (m), change in quality of life score (points), and change in hemoglobin (g/dL), serum ferritin (ng/ml), and transferrin saturation (%). The change in the primary and secondary endpoints from baseline to week 4 will be compared between the two treatment arms by two-sided two sample t-test or Wilcoxon rank sum test. Significance will be decided at alpha=0.05.

We will also construct multivariable regression models with treatment assignment as the main predictor and the change in the primary or secondary endpoint as the outcome variable while adjusting for patients' characteristics such as baseline value of the endpoint, age, sex, ethnicity, hemoglobin level, and measures of disease severity and their interactions with the treatment assignment if necessary. Pre-specified subgroup analyses are based on median age, sex, heart failure etiology (ischemic vs. non-ischemic), NYHA functional Class, median serum ferritin level, and sex-stratified median hemoglobin level.

**Missing Data Consideration:** We anticipate a low percentage of missing data due to the short duration of the study and relatively small data set. The missing data will be handled by intent-to-treat analysis in principle, with last value carried forward. We will compare baseline data in subjects with and without missing data to identify factors contributing to missingness. As sensitivity analyses, a "per protocol" analysis, and analysis with multiple imputation will be undertaken with five imputed datasets using the NORM software. Parameter estimates and their standard errors will be derived by averaging across the five imputations and by adjusting for their variance.

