### 4.14: Sample size calculation:

Our pilot data demonstrated that the post-exercise phosphocreatine recovery time constant decreased by >10 seconds in all 3 non-anemic HF subjects with functional iron deficiency who received ferric carboxymaltose with mean $\pm$ SD decrease  $11.4\pm3.4$  seconds. Table 2 presents the minimal detectable difference between treatment groups over time based on estimates of a range of standard deviations of the between-group

difference and assuming 0-20% dropout, power=0.90, two-tailed alpha=0.05. Table 2 indicates that the proposed sample size provides adequate power to detect moderate to large changes in the post-exercise phosphocreatine recovery time, even when accounting for 20% drop-out. A 10-second change in phosphocreatine recovery time is likely meaningful, since our pilot data suggest that a 10-second decrease would place many HF subjects back to the normal or near normal range. The sample size of 16 subjects per treatment arm will provide >80% power to detect a 35 m difference in six minute walk distance (consistent with a moderate improvement in submaximal exercise capacity, based on data from FAIR-HF and other assumptions as above) and a 20-point difference in the KCCQ score (consistent with a large improvement in health status, based on previous data from FAIR-HF and other assumptions as above).

Table 2. Estimates of minimal detectable between-group difference for post-exercise phosphocreatine recovery time based on power 0.9 with 2-tailed alpha=0.05.

Drop-out Rate	N/group at 4 weeks	Detectable Difference (proportion of SD)	Estimated SD of between group difference (seconds)	Minimal Detectable Difference (seconds)
0%	16	1.15	2	2.3
			4	4.6
			6	6.9
			8	9.2
20%	13	1.3	2	2.6
			4	5.2
			6	7.8
			8	10.4

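### Five imputed datasets leave avoidable simulation noise in the multiple-imputation sensitivity analysis; at least 50, with small-sample degrees of freedom, would remove most of it at almost no cost

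*Combined protocol and SAP*

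**What the plan says.** The paragraph on missing data, under the analysis plan for primary and secondary endpoints, sets out two layers. In the main analysis, missing values are to be "handled by intent-to-treat analysis in principle, with last value carried forward". A per-protocol analysis and a multiple-imputation analysis then serve as sensitivity analyses. For the second, "analysis with multiple imputation will be undertaken with five imputed datasets using the NORM software", with estimates and standard errors "derived by averaging across the five imputations and by adjusting for their variance". That describes Rubin-type pooling. The paragraph does not state a seed, the variables in the imputation model, the reference degrees of freedom or a tolerance for simulation error.

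On the amount of missing data, the same paragraph says "We anticipate a low percentage of missing data" and gives no figure. The sample-size section works with a range, "assuming 0-20% dropout, power=0.90, two-tailed alpha=0.05", and Table 2 goes from 16 to 13 patients per group.

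The analysis-set section restricts the efficacy set to randomized patients who have a follow-up visit at which the primary endpoint was collected.

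**The concern.** A sensitivity analysis for missing data should show how far the result depends on the handling of the missing values. Its answer should not also depend appreciably on the random numbers used. With five imputations the between-imputation variance is estimated on four degrees of freedom, so both the pooled estimate and its standard error move from run to run. If the result lies near 0.05, a rerun of the same stated procedure on the same data can fall on the other side of the line. The plan offers no seed by which a reader could reproduce the run that was reported.

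A second, smaller gap is that the plan speaks of adjusting for variance but does not say which degrees of freedom go with the pooled standard error. At this sample size the choice shifts the p-value.

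**Working it through.** **Inputs from the plan.** Five imputations; 32 patients, 16 per arm (Study Objectives and the sample-size section; Study Design says 36 in one place, and 32 is used here); drop-out 0–20%; two-sided alpha 0.05.

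**Assumed, because the plan is silent.** Values missing at random; normal data; equal missingness per arm; imputation from arm and baseline; the baseline-outcome correlation; the true effect.

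**1. The plan's own figure.** The documents give no figure for imputation error. Table 2 does confirm the drop-out scenario. Detectable difference = √(2/n) × (1.960 + 1.282):
- n = 16: 0.3536 × 3.242 = 1.146 SD (Table 2: 1.15)
- n = 13: 0.3922 × 3.242 = 1.271 SD (Table 2: 1.3)

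Table 2 reproduces. Its 20% case is 3 missing per arm, 6 of 32 values.

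**2. Where the noise comes from.** Let B be the between-imputation variance, T the total variance and γ = B/T, roughly the fraction of missing information. Over reruns, the SD of the pooled estimate in units of its own standard error is √(γ/m). In the simulations the fraction ran from about 0.05 to 0.20.
- m = 5: √(0.05/5) = 0.10 to √(0.20/5) = 0.20
- m = 50: √(0.05/50) = 0.032 to √(0.20/50) = 0.063

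The estimate of B adds noise to the standard error. Its relative SD is √(2/(m−1)), which is 0.71 at m = 5 and 0.20 at m = 50. The sample size appears in neither expression.

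**3. How often a rerun crosses 0.05.** Trials with 16 per arm were simulated, imputed by proper normal regression and pooled with Barnard-Rubin degrees of freedom. The verdict at m = 5 was compared with that of a large-m reference on the same data.

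With ANCOVA, correlation 0.6 and reference p 0.02–0.10:

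| Missing per arm | m = 5 | m = 50 |
|---|---|---|
| 1 | 15–18% | about 5% |
| 3 | 24–31% | 9–11% |

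At m = 100, with 3 missing per arm, the rate is 7–8%. In one such set of runs with 3 missing per arm (mean reference p 0.048), the average 95% spread of p over reruns was 0.017–0.150 at m = 5 and 0.035–0.066 at m = 50.

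With a t-test on change and a correlation of baseline with change of 0 or −0.5, the rates at m = 5 were:

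| Reference p | 1 missing per arm | 2 per arm | 3 per arm |
|---|---|---|---|
| 0.025–0.10 | 15–18% | 21–23% | 26–30% |
| 0.03–0.07 | 23–25% | 30–33% | 36–38% |

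For reference p 0.045–0.055 the rate is 42–47% whatever the missingness, because a result on the line falls either way almost at random.

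**4. Averaged over all simulated trials, not only borderline ones, at m = 5.** About 1–2% with 1 missing per arm under the null and at the Table 2 effects. With 3 per arm: 1.5% under the null, 3.8% at 1.3 SD and 6.3% at 1.15 SD. A weaker effect of 0.6 SD gives 4.5–8.5%, and a very large one (2 SD, 3 missing per arm) gives 0.1%.

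**5. Degrees of freedom.** Complete-data degrees of freedom are 32 − 2 = 30. Rubin's large-sample value is (m−1)/λ², with λ the missing-information fraction. Barnard-Rubin combines this with (31/33) × 30 × (1−λ), by adding reciprocals.
- λ = 0.10: 4/0.01 = 400; (31/33) × 30 × 0.90 = 25.4; combined 23.9
- λ = 0.19: 4/0.0361 = 111; (31/33) × 30 × 0.81 = 22.8; combined 18.9

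A p-value of 0.050 on the large-sample value becomes 0.061 and 0.062 respectively. This is where the small trial matters.

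**The case against.** The strongest objection is that, for the primary endpoint, there may be nothing to impute. The efficacy set admits only patients with follow-up primary-endpoint data, and the schedule has one follow-up visit. Read literally, drop-outs are outside the set, and with no missing outcomes the crossing rate is 0%. This stands as a limit on present effect. It does not remove the point: the plan still commits to the imputation, walk distance, questionnaire and laboratory values can be missing within that set, and if the set is widened to all randomized patients the analysis applies fully.

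Three stronger readings are tempting, and the documents do not support them:
- A reader might infer that more than a quarter of reruns would change the trial's conclusion. That rate needs both a borderline result and the top of the drop-out range. The plan expects less missing data, and most simulated trials are not borderline.
- A reader might infer that this analysis could overturn the primary result. No such rule exists. "Significance will be decided at alpha=0.05" follows the description of the "two-sided two sample t-test or Wilcoxon rank sum test"; for the imputation the plan promises only pooled estimates and standard errors.
- A reader might blame the 32 patients. Step 2 shows that the seed dependence comes from the number of imputations and the missing information.

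It is also fair to say that more imputations cannot stabilise a result lying exactly on 0.05. They narrow the zone in which the seed matters.

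**Conclusion.** The point holds as a minor, easily removed weakness. Five imputations leave simulation noise of about 0.10–0.20 standard errors in the pooled estimate, and m = 50 reduces that about threefold (√10 = 3.2). The chance of crossing 0.05 on a rerun should be quoted only as a range together with its p-value band and missingness, as in the working; no single percentage is a property of this plan. The size rests on data missing at random, normality, equal missingness per arm and an assumed correlation, none of which the documents give. The primary test itself is unaffected.

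**What to change.** In the missing-data paragraph, replace the five imputed datasets by at least 50 (100 is trivial at this size). Fix and record the seed, state that the imputation model contains treatment arm and the baseline value, and specify Barnard-Rubin small-sample degrees of freedom with the variance pooling already described. The last item belongs with the first: raising m makes the large-sample degrees of freedom larger still (49/0.01 = 4,900 at λ = 0.10), even further from the 30 available.

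Reconcile the efficacy-set definition with this paragraph so that randomized patients with a missing outcome are in the set to which imputation applies. Without that, the change acts only on secondary endpoints.

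The imputation change costs one sentence and seconds of computing. It needs no extra data or patients.

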### 4.14: Sample size calculation:

Our pilot data demonstrated that the post-exercise phosphocreatine recovery time constant decreased by >10 seconds in all 3 non-anemic HF subjects with functional iron deficiency who received ferric carboxymaltose with mean $\pm$ SD decrease  $11.4\pm3.4$  seconds. Table 2 presents the minimal detectable difference between treatment groups over time based on estimates of a range of standard deviations of the between-group

difference and assuming 0-20% dropout, power=0.90, two-tailed alpha=0.05. Table 2 indicates that the proposed sample size provides adequate power to detect moderate to large changes in the post-exercise phosphocreatine recovery time, even when accounting for 20% drop-out. A 10-second change in phosphocreatine recovery time is likely meaningful, since our pilot data suggest that a 10-second decrease would place many HF subjects back to the normal or near normal range. The sample size of 16 subjects per treatment arm will provide >80% power to detect a 35 m difference in six minute walk distance (consistent with a moderate improvement in submaximal exercise capacity, based on data from FAIR-HF and other assumptions as above) and a 20-point difference in the KCCQ score (consistent with a large improvement in health status, based on previous data from FAIR-HF and other assumptions as above).

Table 2. Estimates of minimal detectable between-group difference for post-exercise phosphocreatine recovery time based on power 0.9 with 2-tailed alpha=0.05.

Drop-out Rate	N/group at 4 weeks	Detectable Difference (proportion of SD)	Estimated SD of between group difference (seconds)	Minimal Detectable Difference (seconds)
0%	16	1.15	2	2.3
			4	4.6
			6	6.9
			8	9.2
20%	13	1.3	2	2.6
			4	5.2
			6	7.8
			8	10.4

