## PRELIMINARY DATA

We measured post-exercise phosphocreatine recovery time as a validated index of skeletal muscle mitochondrial oxidative capacity with a novel spectrally selective three-dimensional turbo spin echo (3D-TSE) 31P MRS/MRI protocol developed at NYU School of Medicine in eight non-anemic HF patients and five non-heart failure control subjects. In three of the HF patients with functional iron deficiency, the 31P MRS/MRI protocol was repeated one week after a single dose of ferric carboxymaltose 500 mg. In agreement with previous studies using surface coils, we showed that the post-exercise phosphocreatine recovery time was prolonged in HF subjects when compared with control subjects (Figure 1), both for the whole muscle of the lower extremity (MRS Global and MRI Global) and also for individual muscle groups. In three HF subjects with functional iron deficiency, intravenous administration of ferric carboxymaltose 500 mg increased serum ferritin (mean 67 to 783 ng/mL), increased 6-minute walk distance (mean 342 to 369 m), decreased post-exercise phosphocreatine recovery time (mean 51 to 39 seconds, Figure 3), but did not change hemoglobin level (mean 14.6 to 14.0 g/dL). Intravenous iron was well-tolerated. There were no adverse events related to study drug or study procedures. These data were presented in abstract form at the 2015 International Society for Magnetic Resonance in Medicine meeting.

**Significance:** Abnormal iron homeostasis due to chronic inflammation and/or nutritional deficiencies affects over 1 billion persons worldwide. Functional iron deficiency is present in 50% of heart failure patients and is associated with more severe symptoms and greater risk for adverse outcomes with or without anemia. Although the effects of iron deficiency on erythropoiesis are well characterized, there are no existing human data on the impact of iron deficiency on skeletal muscle metabolism, and only limited data on the extra-medullary biological effects of intravenous iron therapy.

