## STUDY OBJECTIVES

A single-center, prospective double-blind parallel group randomized study is proposed to compare the effects of ferric carboxymaltose vs. placebo on skeletal muscle mitochondrial oxidative capacity, submaximal exercise tolerance, and health-related quality of life in HF patients with functional iron deficiency. The goal of this study is to provide novel “proof-of-concept” data to demonstrate biological plausibility to support the use of ferric carboxymaltose in HF patients and other disease populations with functional iron deficiency.

32 eligible subjects will be randomly assigned (1:1) to ferric carboxymaltose 750 mg or placebo (normal saline) and will undergo serial assessment before and 4 weeks after study drug administration to address the following study endpoints:

**Primary Endpoint:** To compare the effects of ferric carboxymaltose 750 mg vs. placebo on change in skeletal muscle mitochondrial oxidative capacity from baseline to 4 weeks (post-exercise phosphocreatine recovery time measured non-invasively with 31P-magnetic resonance spectroscopy).

[figure not shown]

Figure 1. Mean $\pm$ SEM data for comparison of global (31P-MRS) and regional (31P-MRI, gastrocnemius medial (GM), gastrocnemius lateral (GL), and soleus muscle (SOL)) post-exercise PCr recovery time constant between 5 healthy control subjects (blue bars) and 8 HF subjects (red bars).

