## STUDY DESIGN

The proposed study design is a prospective, single-center, randomized, double-blind, parallel group placebo-controlled study (Figure 2). Primary and secondary endpoints will be assessed before and 4 weeks after administration of ferric carboxymaltose or placebo. It is anticipated that the study will require 2 years to complete enrollment.

**Study population:** Up to 50 subjects will be recruited from the clinical practice of the NYU Advanced Cardiac Therapeutics group at NYU Langone Medical Center. 36 eligible subjects will be randomized. Study entry criteria are listed in the Human Subjects section below.

**Study visits:** The study will require 3 visits over approximately 8-10 weeks for each subject: Visit 1: Screening; Visit 2: Baseline primary and secondary endpoint measurements, randomization, and study drug administration; Visit 3: final assessment of primary and secondary endpoint measurements. Additional details of the procedures at each study visit are described below.

**Study agent and control description:** Ferric Carboxymaltose (Injectafer®, 750 mg iron/15 ml sterile single use vial) will be provided by the American Regent pharmaceuticals (Shirley, NY) to the NYU Investigational Pharmacy and stored in the NYU Investigational pharmacy at 20°C to 25°C according to manufacturer instructions. An IND exemption will be requested from the FDA. Ferric carboxymaltose is nonionic polynuclear iron (III) hydroxide carbohydrate complex that binds iron tightly and requires macrophage processing for release of iron into body stores. Ferric carboxymaltose has been demonstrated to be safe and effective in the treatment of iron deficiency anemia and is FDA-approved for treatment of iron deficiency in adult patients. The most common adverse reactions recorded in clinical trials (>2%) are nausea, hypertension, flushing, hypophosphatemia, and dizziness. The dosing and route of administration used in this study protocol are consistent with the FDA-approved prescribing information for this drug (see appendix for FDA-approved package insert) and prior studies of this agent in heart failure populations.

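### The sample size section claims adequate power for the primary endpoint without qualification, but Table 2 supports it only for differences above about 1.2 to 1.3 SD and only for an SD whose range has no stated source

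*Combined protocol and SAP*

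**What the plan says.** Section 4.14 (Sample size calculation) sets "power=0.90, two-tailed alpha=0.05" and tabulates the detectable difference in phosphocreatine recovery time for SDs of 2, 4, 6 and 8 s. It does so at 16 per arm (no drop-out) and 13 per arm (20% drop-out). From this it concludes that "the proposed sample size provides adequate power to detect moderate to large changes in the post-exercise phosphocreatine recovery time", and that this still holds after 20% drop-out. The next sentence gives the only effect size for this endpoint that is assigned a meaning: "A 10-second change in phosphocreatine recovery time is likely meaningful".

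The same section reports a pilot decrease of 11.4 s with SD 3.4 s in three treated, non-anemic patients, each with a decrease above 10 s. Under Preliminary Data, their scan was "repeated one week after a single dose of ferric carboxymaltose 500 mg". The trial itself gives 750 mg or placebo, with "serial assessment before and 4 weeks after study drug administration" (Study Objectives). The planned comparison of change is a "two-sided two sample t-test or Wilcoxon rank sum test" (Analysis plan for primary and secondary endpoints).

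**The concern.** The adequacy statement carries no condition, yet it depends entirely on the SD of individual 4-week change, which the documents do not establish. The table stops at 8 s and gives no reason for stopping there. No placebo-arm SD and no scan-to-scan repeatability figure is given. The one SD available has two degrees of freedom and comes from a different dose and a different interval.

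The wording also sits poorly with the table. Its own column in SD units shows that 90% power begins only above one SD, which is a demanding reading of a moderate change.

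This is a proof-of-concept trial. If the SD is 10 to 12 s, a true 10-s effect would be missed 22% to 47% of the time (1 − 0.78 with 16 per arm at SD 10 s; 1 − 0.53 with 13 per arm at SD 12 s). Readers told that power was adequate would be inclined to take a null result as evidence against the mechanism.

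**Working it through.** **Inputs.** Two-sided alpha 0.05, power 0.90, SDs of 2 to 8 s, 16 or 13 per arm, pilot mean 11.4 s and SD 3.4 s, and a 10-s difference (all section 4.14); 1:1 allocation of 32 (Study Objectives). The SD must be read as the per-patient SD of change for Table 2's formula to work. SDs above 8 s are my assumptions.

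**1. Reproduce Table 2.** Normal approximation: detectable difference in SD units = (1.960 + 1.282) × √(2/n).

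- n = 16: 3.242 × 0.3536 = 1.146 (printed 1.15)
- n = 13: 3.242 × 0.3922 = 1.271 (printed 1.3)

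The seconds column follows: 8 × 1.15 = 9.2 and 8 × 1.3 = 10.4. The table reproduces.

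**2. The same quantity for the planned t-test.** Power = P(T > t₀.₉₇₅) with 2n − 2 df and noncentrality (difference/SD) × √(n/2). Solving for 90% gives 1.185 SD (n = 16) and 1.326 SD (n = 13).

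**3. Last row of the table.** SD 8 s, n = 13, difference 10 s: noncentrality = 1.25 × √6.5 = 3.19. Power is 86% by t and 89% by the normal approximation. The detectable difference is 10.2 s (normal), 10.4 s (printed) or 10.6 s (t).

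**4. Power for 10 s across SDs (t-test).**

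| SD of change (s) | Power, 16/arm | Power, 13/arm | 90% detectable difference, 16 / 13 per arm (s) |
|---|---|---|---|
| 6 | 99.5% | 98% | 7.1 / 8.0 |
| 8 | 93% | 86% | 9.5 / 10.6 |
| 10 (assumed) | 78% | 69% | 11.9 / 13.3 |
| 12 (assumed) | 63% | 53% | 14.2 / 15.9 |

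The SD 10 s row is also the power for a difference of exactly one SD.

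**5. Largest SD that keeps 90% power for 10 s.**

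- t-test: 10/1.185 = 8.4 s (16 per arm) and 10/1.326 = 7.5 s (13 per arm)
- Table 2's printed multipliers: 10/1.15 = 8.7 s and 10/1.3 = 7.7 s

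**6. What the pilot SD can support.** If three decreases all exceed 10 s and average 11.4 s, the SD is largest near 10, 10 and 14.2. The deviations are −1.4, −1.4 and 2.8, so SD = √[(1.96 + 1.96 + 7.84)/2] = √5.88 = 2.4 s. The printed 3.4 s is therefore incompatible with the sentence around it.

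On 2 df and assuming normality, the one-sided 90% upper limit is SD × √(2/0.2107) = SD × 3.08. That is 10.5 s from 3.4 s, but at most 7.5 s from 2.42 s. The two results fall on either side of the table's 8-s ceiling, so the pilot neither justifies nor refutes that ceiling.

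**The case against.** The strongest reply is that Table 2 is already a conditional statement: it shows a range of SDs, reaches about 2.4 times the printed pilot SD (8/3.4), and gives the differences in SD units. That is true, and the table itself is not at fault. The sentence that interprets the table is what drops the condition.

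Several stronger readings are tempting, and the documents do not support them:

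- **Table 2 is miscalculated.** It is not; step 1 reproduces it. The normal approximation is slightly optimistic for a t-test at this size, and no more than that.
- **The trial misses its 10-s target.** Section 4.14 calls 10 s likely meaningful. It does not name a target, nor does it say that every row covers it. The shortfall is in one row of eight, 0.4 s as printed. Since the section uses power above 80% for its secondary endpoints, 86% could fairly be called adequate.
- **The 2 to 8 s range was taken from the pilot.** The protocol does not say so. It gives no source at all.
- **The pilot shows that the SD may well exceed 10 s.** An upper limit of 10.5 s, or a two-sided 95% limit of 21.4 s, follows only from the 3.4 s figure, which step 6 shows to be doubtful.
- **Moderate is demonstrably wrong.** The section defines moderate neither in seconds nor in SD units, so the word is unsupported by the table rather than contradicted by a stated definition.

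The number randomized is also unsettled. Study Design says "36 eligible subjects will be randomized", against 32 in the Study Summary and Study Objectives. With 18 per arm and 20% drop-out (about 14 completers), SD 8 s gives 9.8 s (normal) or 10.2 s (t), so the last-row shortfall could disappear. The missing source for the SD would remain.

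**Conclusion.** The point stands as a matter of wording and support, not of arithmetic. The unqualified adequacy claim goes further than Table 2, which shows 90% power only for differences of about 1.15 to 1.3 SD (1.18 to 1.33 SD by the t-test). For a 10-s difference, 90% power holds only if the SD of individual 4-week change is at most about 8.4 s with 16 per arm or 7.5 s with 13 per arm. Just beyond the table's range, power falls to 78% / 69% at SD 10 s and 63% / 53% at SD 12 s.

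These figures assume a t-test with equal, normally distributed variation in both arms and 16 or 13 completers per arm; the Wilcoxon alternative was not evaluated. Whether the true SD lies above 8 s cannot be determined from the documents. A reader should not infer that the trial is underpowered or needs more patients, only that its power is less certain than section 4.14 says.

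**What to change.** In section 4.14:

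1. Replace the adequacy sentence with a conditional one, for example: *90% power for a 10-s difference holds only if the SD of individual 4-week change is at most about 8.4 s (16 per arm) or 7.5 s (13 per arm); at SD 10 s power is 78% / 69%, and at SD 12 s 63% / 53%.*
2. Recompute Table 2 with the t-test multipliers (1.185 and 1.326, or 1.18 and 1.33 to two decimals). Otherwise the new sentence would clash with the printed multipliers, which imply 8.7 and 7.7 s.
3. Add rows for SDs of 10 and 12 s, labelled as assumptions, and give the basis for the 2 to 8 s range or label it as assumed too.
4. Replace the moderate-to-large wording with *differences larger than about 1.2 to 1.3 SD*.
5. Reconcile the pilot SD of 3.4 s with the statement that all three decreases exceeded 10 s around a mean of 11.4 s.

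The cost is a recomputed table with added rows for two SDs and a few sentences. No patients are added and the design is unchanged. The downside is a less favourable, conditional power statement.
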